#### 11.4.4. Control of Multiplicity

The overall type I error rate will be controlled for the primary hypothesis at the two-sided 0.05 level by the use of a step-down testing approach, starting at the top dose (Table 4). Each test compares a specific treatment group to pooled placebo. The highest dose will be tested first; if significant, the second highest dose will be tested; and so on. No multiplicity adjustments will be made for secondary endpoints, nor for comparisons between active doses.

Table 4: Statistical Testing Hierarchy

Hierarchy Number	Description
1	2400 mg IV versus pooled placebo
2	1200 mg IV versus pooled placebo
3	1200 mg SC versus pooled placebo
4	600 mg IV versus pooled placebo
5	600 mg SC versus pooled placebo
6	300 mg IV versus pooled placebo

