5.7.1. Analysis of Primary Efficacy Variable

The primary virologic efficacy variable is the time-weighted average change from baseline in viral load from day 1 to day 7, as measured by RT-qPCR in NP swab samples. The primary analysis will be conducted in the Seronegative mFAS population. An Analysis of Covariance (ANCOVA) model with treatment group as a fixed effect and baseline viral load and treatment by baseline interaction as covariates will be fit to the data as the primary analysis. For efficacy analysis, the placebo IV and placebo SC arms are pooled.

A step-down testing approach will be used for comparing active treatment groups to the pooled placebo to control type I error rate at 0.05. The pairwise comparisons are performed using the t-

test. [Figure 2](#) below illustrates this hierarchy. If a test is insignificant, then the formal testing procedure stops at that step.

Figure 2: Testing Hierarchy

The least squares mean estimates and 95% confidence intervals for the TWA mean change from baseline in viral load will be presented for each treatment group, as well as for the difference between each REGN10933+REGN1097 treatment group and placebo along along with the p-values for the comparisons. Accompanying descriptive analyses will be provided at the individual timepoints used to calculate the TWA.

No hypothesis testing is planned for the between active dose comparisons. Only estimates and 95% confidence intervals will be reported for the between active dose comparisons.

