5.7.5. Analysis of Secondary Efficacy Variables

For the analysis of primary and secondary efficacy variables, the table below summarizes the quantities and corresponding methods for analysis. The details of methods are described the paragraphs that follow.

Table 5: Secondary Efficacy

Measurement	Units	Metric	Method
Viral load (D1-5)	log ₁₀ copies/mL	TWA	ANCOVA
Viral load	log ₁₀ copies/mL	Change from BL in viral load at each visit	MMRM
Viral load	log ₁₀ copies/mL	Proportions <LLOQ, <LOD, >10 ⁴ , >10 ⁵ , >10 ⁶ , or >10 ⁷	Fisher's Exact Test/Logistic Regression
Percent change in Viral Load	copies/mL	Percent change in viral load (copies/mL) to each time point	MMRM

A mixed effect model for repeated measures (MMRM) will assess the time course of treatment effect in viral load, the change from baseline in viral load (log₁₀ copies/mL) at each visit for both the Seronegative mFAS and the Overall mFAS populations. The model will include terms for baseline, treatment, visit, treatment-by-baseline interaction, baseline-by-visit interaction, and treatment-by visit interaction. Within-patient errors will be modeled with an unstructured covariance matrix; heterogeneous autoregressive (1), or compound symmetry covariance matrix will be considered in that order if a model does not converge. The least squares means estimates for the mean at each visit and mean change from baseline to each visit as well as the difference of these estimates between each anti-spike mAb treatment arm and placebo will be provided along with the corresponding standard error, p-value, and associated 95% confidence interval.

In the Seronegative mFAS, the proportion of patients who have PCR below the limit of detection (LOD), below the lower limit of quantification (LLOQ), or have qPCR levels >10⁴, >10⁵, >10⁶, or >10⁷ will be tabulated over time. The numbers of patients in each category will be tested using Fisher's Exact test. Corresponding p-values and confidence intervals will be presented.

There may be additional analysis of the proportions of patients who have PCR below the limit of detection, below the lower limit of quantification, or have quantitative PCR levels above >10⁴, >10⁵, >10⁶, or >10⁷ will be tabulated over time using logistic regression model with terms for treatment arm, baseline viral load, and the treatment-by-baseline viral load interaction. Adjusted odds ratios and corresponding p-values and confidence intervals may be estimated from the model.

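### The viral-load proportion endpoints are tested with an unadjusted, conservative Fisher's exact test, and the baseline-adjusted model is optional and incompletely specified

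*SAP*

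**What the plan says.** SAP 5.7.5 covers six binary outcomes at each visit in the Seronegative mFAS: below LOD, below LLOQ, and above 10^4, 10^5, 10^6 and 10^7 copies/mL. Of these it states: "The numbers of patients in each category will be tested using" Fisher's exact test, with p-values and confidence intervals to follow. Protocol 11.4.3.2 carries the same sentence and names no adjusted model.

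A further SAP paragraph begins "There may be additional analysis of the proportions of patients who have PCR below the limit of detection" and describes a "logistic regression model with terms for treatment arm, baseline viral load, and the treatment-by-baseline viral load interaction". It closes: "Adjusted odds ratios and corresponding p-values and confidence intervals may be estimated from the model". Both the analysis and its reporting are therefore optional. SAP Table 5 gives Fisher's test and logistic regression side by side as the method for these proportions, without marking either as optional.

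The continuous virologic endpoints are handled differently. In the primary ANCOVA (SAP 5.7.1), "baseline viral load and treatment by baseline interaction as covariates will be fit to the data as the primary analysis". For the by-visit MMRM (SAP 5.7.5), "The model will include terms for baseline, treatment, visit, treatment-by-baseline interaction, baseline-by-visit interaction, and treatment-by visit interaction".

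Type I error is "controlled for the primary hypothesis at the two-sided 0.05 level" (Protocol 11.4.4). The same section adds: "No multiplicity adjustments will be made for secondary endpoints, nor for comparisons between active doses".

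**The concern.** The proportions come from the same assay, swabs and patients as the continuous endpoints. Whether a patient is above a threshold at day 3, 5 or 7 is likely to depend on where that patient started. The plan requires baseline adjustment for the ANCOVA and MMRM and gives no reason for leaving it out here.

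Three things follow.

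- **Power.** Fisher's test is conservative at these sample sizes and gains nothing from a covariate that the trial already measures.
- **Flexibility.** The text and Table 5 do not agree on whether the logistic model is part of the plan. The decision to run and report it could be taken after unblinding.
- **Specification.** With a treatment-by-baseline interaction, the odds ratio changes with baseline viral load. The SAP does not say at which baseline value, or by what averaging, it will be reported.

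At stake is how informative the secondary proportion tables are for each active arm against pooled placebo.

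**Working it through.** **The plan's own figure.** No power is stated for the proportions. The only stated power (Protocol 11.2, SAP 2.2) is about 98% for the TWA endpoint with 57 per group, difference 0.73 and SD 0.948. The standard error is 0.948 × √(2/57) = 0.1776, so 0.73/0.1776 = 4.11, and power = Φ(4.11 − 1.96) = 98.4%. The figure reproduces. It concerns the primary endpoint only.

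**Inputs from the documents.** Group sizes are 57 and 100 (SAP 2.2). Each active arm is allocated 1:1 to pooled placebo (SAP 2.1). Two-sided 0.05 is taken over from the primary hypothesis.

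**Assumed inputs.** The documents give no threshold proportions, no baseline SD and no baseline-to-visit correlation (rho). Three pairs of proportions above threshold were assumed (placebo vs active): 57% vs 38.5%, 50% vs 30% and 30% vs 12%. The first corresponds to log10 SD 1.7, a shift of 0.8 and a threshold of 4.0. Rho was set to 0, 0.3, 0.5 and 0.7.

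**Method.** The later viral load is latent normal with correlation rho to baseline, and is dichotomised at the threshold. Three tests were compared:

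- Fisher's exact test
- unadjusted chi-square
- the likelihood-ratio test for treatment in a logistic model with treatment and baseline as main effects

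There were 5,000 simulated trials per setting for the first pair and 1,500 for the other two. Monte Carlo error is about 1.3 points or less per power.

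Power in %, Fisher / chi-square / adjusted logistic:

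| n per arm | Proportions | rho 0 | rho 0.3 | rho 0.5 | rho 0.7 |
|---|---|---|---|---|---|
| 57 | 57 vs 38.5 | 42.5 / 49.9 / 50.5 | 42.1 / 49.4 / 52.8 | 42.7 / 51.2 / 59.4 | 43.5 / 51.1 / 68.2 |
| 57 | 50 vs 30 | 53.7 / 61.0 / 61.3 | 50.9 / 58.8 / 63.8 | 50.1 / 58.1 / 65.0 | 50.0 / 59.0 / 76.7 |
| 57 | 30 vs 12 | 57.9 / 67.4 / 68.3 | 60.0 / 68.7 / 70.7 | 57.3 / 66.5 / 73.1 | 58.6 / 67.8 / 81.9 |
| 100 | 57 vs 38.5 | 71.8 / 76.6 / 75.7 | 71.1 / 75.7 / 77.4 | 72.8 / 77.4 / 82.8 | 71.7 / 76.3 / 89.0 |
| 100 | 50 vs 30 | 79.4 / 82.8 / 82.9 | 78.5 / 83.3 / 85.3 | 79.9 / 83.7 / 89.3 | 78.7 / 82.4 / 94.3 |
| 100 | 30 vs 12 | 83.6 / 88.4 / 88.3 | 86.0 / 90.5 / 91.1 | 83.3 / 87.5 / 92.5 | 85.2 / 88.9 / 96.3 |

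**Total gap, Fisher to adjusted logistic, rho 0.3 to 0.7.** At 57 per arm it runs from 10.7 points (70.7 − 60.0) to 26.7 (76.7 − 50.0). At 100 per arm it runs from 5.1 (91.1 − 86.0) to 17.3 (89.0 − 71.7).

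**Splitting the gap.** Fisher to chi-square isolates conservatism, because neither test uses baseline.

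- At 57 per arm conservatism costs 7.3 to 9.5 points and is present at rho 0. At 100 per arm it costs 3.4 to 4.8.
- Chi-square to adjusted logistic isolates the baseline term. At 57 per arm it adds 2.0 to 5.0 points at rho 0.3, 6.6 to 8.2 at rho 0.5 and 14.1 to 17.7 at rho 0.7.

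**Type I error** (50% in both arms, 57 per arm). Fisher's test rejects 2.7% to 4.1% of the time, chi-square 4.8% to 5.8%, and the adjusted likelihood-ratio test 5.1% to 6.1%.

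**The SAP's optional interaction model**, tested by Wald at mean baseline with 57 per arm, is not a safe substitute. At 30% vs 12% and rho 0.7 it has 46.5% power against 58.6% for Fisher. At 10% vs 2%, where events are sparse, it has 0% to 6% against 24% to 27%.

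**The case against.** The strongest reply is that Fisher's test is valid and that these endpoints do not carry the dose decision. They are secondary, outside the testing hierarchy and not adjusted for multiplicity. Six outcomes × five post-baseline swab visits (days 3, 5, 7, 15, 22) × six active arms gives up to 180 tests against placebo in the Seronegative mFAS alone, and a slightly conservative test is defensible there. This stands, and it is why the point is minor.

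The power figures rest on assumed proportions and correlations, and at rho 0.3 the baseline term alone is worth little. This also stands.

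A sparse-data fallback would often return the analysis to Fisher. With a rule of fewer than 5 events or non-events in either arm, and assumed proportions, it would trigger in 99.6% of cases at 57 per arm and 95% at 100 for 10% vs 2%; in 85% and 44% for 15% vs 5%; and in 17% and under 1% for 30% vs 12%. The improvement therefore falls mainly on thresholds and visits with moderate proportions. A per-arm rule could also switch methods between doses, so the rule has to be framed differently.

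An interaction model can give a single odds ratio at a stated baseline value. That is correct; the gap is that the SAP states none.

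A reader might infer that a low dose that clears virus would be judged no different from placebo. The documents do not support that: the formal dose-versus-placebo conclusions come from the TWA hierarchy, with about 98% power, beside the MMRM and dose-response modelling. A reader might also infer that these proportions are the only analysis without a baseline term. They are not: the dose-response models in SAP 5.7.4 contain dose alone.

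**Conclusion.** The point holds as a modest inefficiency and a gap in specification. The required test for the proportions is conservative and ignores baseline viral load; the adjusted alternative is optional in the text, inconsistent with Table 5 and lacks a defined estimate.

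Under the assumed proportions and correlations of 0.3 to 0.7, the loss is about 11 to 27 points of power at 57 per arm and about 5 to 17 at 100 per arm. It would be wrong to attribute all of this to omitting baseline: about 7 to 10 points at 57 per arm, and about 3 to 5 at 100, are Fisher's conservatism and would remain if baseline were uninformative. The baseline share is large only near a correlation of 0.7. The direction does not depend on the scenario, since Fisher was the weakest of the three tests in every setting in the table; the size does.

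Fisher's rejection rate below 5% is not an error, and the primary conclusion is not affected.

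**What to change.** Make logistic regression with treatment and baseline log10 viral load as main effects, without the interaction, the prespecified analysis of these proportions. Report a standardised risk difference with 95% CI beside the adjusted odds ratio. Amend Table 5 and the text of SAP 5.7.5 to agree. Because Protocol 11.4.3.2 also names Fisher's test, record the change in SAP 1.2.5, which now lists no departures from the protocol.

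Keep Fisher's exact test as the prespecified fallback for sparse cells or non-convergence. Fix the sparse-data rule in advance on pooled, blinded counts for each visit and threshold. Fitting all seven groups in one model, and moving all six comparisons to Fisher together if it fails, keeps the method the same across doses.

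The cost is SAP wording and modest programming, with no new data. It should be settled before unblinding; afterwards it could only be labelled post hoc. There are three downsides:

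- The fallback will often apply at high thresholds and late visits.
- The odds ratio is conditional on baseline, so it will not match the raw proportions; hence the risk difference.
- The adjusted likelihood-ratio test can run slightly above 5% (about 6%) at 57 per arm.

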5.7.6. Analysis of Other Secondary Efficacy

The table in subsection 4.5.2 describes the other secondary efficacy variables. All variables will be tabulated.

5.8. Analysis of Safety Data

The analysis of safety and tolerability will be performed in the SAF population.

5.8.1. Adverse Events

Safety data will be summarized in three periods:

1. The pretreatment period, i.e., from signing the ICF to before the study drug administration
2. The 29-day observation period, i.e., from the time of the administration of the study drug to the last follow-up visit.
3. The full observation period, i.e., from the time of the administration of the study drug to the last follow-up visit.

For patients that are vaccinated for SARS-CoV-2, only the safety data before vaccination will be used in the primary safety analysis. A secondary safety analysis will use all data collected.

Analysis

All SAEs and AESIs reported in this study will be coded using the currently available version of the Medical Dictionary for Regulatory Activities (MedDRA[®]). Coding will be to lowest level terms. The preferred term (PT), and the primary system organ class (SOC) will be listed.

Summaries by treatment group will include the following:

- The number (n) and percentage (%) of patients with at least 1 treatment-emergent adverse events (AEs) through day 29 by system organ class and PT
- The number (n) and percentage (%) of patients with at least 1 treatment-emergent serious adverse events (SAEs) through day 29 by system organ class and PT
- The number (n) and percentage (%) of patients with at least 1 infusion-related reactions (grade ≥ 2), through day 4 by PT
- The number (n) and percentage (%) of patients with at least 1 injection-site reaction (grade ≥ 3), through day 4 by PT
- The number (n) and percentage (%) of patients with at least 1 hypersensitivity reactions (grade ≥ 2), through day 29 by PT
- Any TEAE that led to a hospitalization or emergency room visit, regardless of whether the visit is related to COVID-19, up to day 169
- Treatment-emergent AEs (grade 3 or 4) from day 30 to day 169
- Treatment-emergent SAEs, up to day 169

Summaries of SAEs and AESIs by treatment group will include:

- The number (n) and percentage (%) of patients with at least 1 event by SOC and PT
- SAEs and AESIs by severity (according to the grading scale described in the protocol), presented by SOC and PT

- SAEs and AESIs by relationship to treatment (related, not related), presented by SOC and PT
- Treatment-emergent SAEs and AESIs
- The number (n) and percentage (%) of patients with Grade 3 or Grade 4 treatment-emergent adverse events.

Deaths and other SAEs will also be listed and summarized by treatment arm. Tables describing the adverse events will be made covering the two periods, except the observation period will be broken into two divisions: day 1 to day 29 and day 1 to day 169.

There will also be lists of every Treatment-Emergent Adverse Event (TEAE). Then there will be a list of TEAEs for the proportion that occurs greater than or equal to 5% and a list of TEAEs for the proportion that occurs greater than or equal to 10%.

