## 10. SAFETY EVALUATION AND REPORTING

### 10.1. Recording and Reporting Adverse Events

#### 10.1.1. General Guidelines

In this study, the following TEAEs will be recorded:

- Treatment-emergent AEs, up to day 29
- Treatment-emergent AESIs (Section 10.1.3) as follows:
  - Grade  $\geq 2$  infusion-related reactions, up to day 4
  - Grade  $\geq 3$  injection-site reactions, up to day 4
  - Grade  $\geq 2$  hypersensitivity reactions, up to day 29
  - Any TEAE that led to a hospitalization or emergency room visit, regardless of whether the visit is related to COVID-19, up to day 169
- Treatment-emergent AEs (grade 3 or 4 only), from day 30 to day 169
- Treatment-emergent SAEs, up to day 169

The investigator must promptly record the above TEAEs occurring during the observation period (see Section 11.4.5.1). Note that the length of this period differs in each study phase, owing to different final study visit days. Medical conditions that existed or were diagnosed prior to the signing of the informed consent will be recorded as part of medical history. Abnormal laboratory values and vital signs observed at the time of informed consent should also be recorded as medical history. Any subsequent worsening (ie, any clinically significant change in frequency and/or intensity) of a pre-existing condition that is temporally associated with the use of the study drug should also be recorded as TEAE, provided that it fulfills the above criteria.

Throughout the study, the investigator will determine whether any TEAEs occurred by evaluating the patient. These events may be directly observed, reported spontaneously by the patient, or by questioning the patient at each study visit. Patients should be questioned in a general way, without asking about the occurrence of any specific symptoms. The investigator must assess all TEAEs to determine seriousness, severity, and causality, in accordance with the definitions in Section 10.2. The investigator's assessment must be clearly documented in the site's source documentation with the investigator's signature. The investigator should follow up on TEAEs until they have resolved or are considered clinically stable.

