### 11.4.5. Safety Analysis

#### 11.4.5.1. Adverse Events

##### Definitions

For safety variables, 3 periods are defined:

- The **pretreatment period** is defined as the time from signing the ICF to before study drug administration
- The **29-day observation period** is defined as the time of study drug administration to day 29.
- The **full observation period** is defined as the time of the administration of the study drug to the last follow-up visit.

Treatment-emergent adverse events are defined as those that are not present at baseline or represent the exacerbation of a pre-existing condition during the observation period.

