##### Analysis

All adverse events reported in this study will be coded using the currently available version of the Medical Dictionary for Regulatory Activities (MedDRA®). Coding will be to lowest level terms. The preferred term (PT), and the primary system organ class (SOC) will be listed.

Summaries by treatment group will include the following:

- The number (n) and percentage (%) of patients with at least 1 treatment-emergent AE through day 29 by SOC and PT
- The number (n) and percentage (%) of patients with at least 1 treatment-emergent grade 3 or 4 AE through day 169 by SOC and PT
- The number (n) and percentage (%) of patients with at least 1 treatment-emergent SAE through day 29 by SOC and PT
- The number (n) and percentage (%) of patients with at least 1 infusion-related reaction (grade  $\geq 2$ ), through day 4 by PT
- The number (n) and percentage (%) of patients with at least 1 injection-site reaction (grade  $\geq 3$ ), through day 4 by PT

- The number (n) and percentage (%) of patients with at least 1 hypersensitivity reaction (grade  $\geq 2$ ), through day 29 by PT

Summaries of SAEs and AESIs by treatment group will include:

- The number (n) and percentage (%) of patients with at least 1 event by SOC and PT
- SAEs and AESIs by severity (according to the grading scale outlined in Section 10.2.5), presented by SOC and PT
- SAEs and AESIs by relationship to treatment (related, not related), presented by SOC and PT
- Treatment-emergent SAEs and AESIs

Deaths and other SAEs will be listed and summarized by treatment arm.

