1.2.5. Modifications from the Statistical Section in the Final Protocol

Not applicable.

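### SAP 5.8.1 gives the 29-day safety period the same end as the full period, and does not limit its day 1–169 adverse-event tables to the event types collected to day 169

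*SAP*

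**What the plan says.** SAP 5.8.1 lists three safety periods. The second is "The 29-day observation period, i.e., from the time of the administration of the study drug to the last follow-up visit". The third is "The full observation period, i.e., from the time of the administration of the study drug to the last follow-up visit". Apart from the label, the two are identical. In Protocol 11.4.5.1 the 29-day period "is defined as the time of study drug administration to day 29". SAP 1.2.5, which should list departures from the protocol's statistical section, reads "Not applicable".

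After its lists of summaries, SAP 5.8.1 says that in the adverse-event tables "the observation period will be broken into two divisions: day 1 to day 29 and day 1 to day 169". It does not say which event types belong in which division. It then asks for lists of treatment-emergent events occurring in at least 5% and at least 10%, with no time window.

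Collection is set in Protocol 10.1.1 and in footnote 5 of Protocol 9.1.1. All-grade recording is "Treatment-emergent AEs, up to day 29". From day 30 to day 169, only grade 3–4 events, serious events, and events leading to hospitalisation or an emergency room visit are recorded.

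For grade 3–4 events, Protocol 11.4.5.1 calls for the number and percentage of "patients with at least 1 treatment-emergent grade 3 or 4 AE through day 169 by SOC and PT". The SAP's windowed item is "Treatment-emergent AEs (grade 3 or 4) from day 30 to day 169". A second SAP item on grade 3 or 4 events gives no window.

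**The concern.** Safety and tolerability is a secondary objective, and the SAP is meant to settle the analysis before database lock and unblinding. Three things are left unsettled.

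- **Period definition.** A programmer who builds the 29-day outputs from the period definition, not from each summary's own limit, would bring in events up to day 169. The exposure is greatest in the second list in SAP 5.8.1 (serious events and events of special interest by severity, relationship and so on), whose items carry no window.
- **Day 1–169 tables and frequency lists.** An any-grade percentage to day 169 would combine event types followed for the whole period with others followed only to day 29, and would read as a 169-day incidence.
- **Grade 3–4 events.** The summary the protocol asks for, from dosing through day 169, is not clearly stated in the SAP.

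**Working it through.** The plan states no figure that can be reproduced on this point. The check compares definitions and windows.

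**1. Period definitions**

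| Period | Protocol 11.4.5.1 ends at | SAP 5.8.1 ends at |
|---|---|---|
| 29-day | day 29 | last follow-up visit |
| Full | last follow-up visit | last follow-up visit |

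The SAP's second row is right and its first row is not. With final follow-up at day 169, the period labelled as 29 days would be 169/29 = 5.8 times its nominal length. This is a ratio of days, not of event percentages.

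**2. Which day-29 outputs depend on that definition**

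In the first list of SAP 5.8.1, the summaries of all adverse events, serious adverse events and hypersensitivity reactions each state day 29. Those of infusion-related and injection-site reactions state day 4. The later text divides the tables by study day, with one division ending at day 29. These outputs therefore have a correct limit that does not rely on period 2.

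**3. Event types and windows**

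| Event type | Collected to (Protocol 10.1.1) | Valid as a day 1–169 percentage? |
|---|---|---|
| Serious events, any grade | day 169 | yes |
| Grade 3–4 events | day 169 | yes |
| Events leading to hospitalisation or emergency room visit, any grade | day 169 | yes |
| All other grade 1–2 events | day 29 | no |

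For the last row, collection covers 29/169 = 17% of the days. It is absent for 169 − 29 = 140 days, and 140/169 = 83%.

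**4. What an any-grade day 1–169 table could show**

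The documents give no event rates, so the following are assumptions: a constant hazard; a day-29 risk a of 5% to 20% for other grade 1–2 events; and a day-29 risk b of 1% to 2% for events collected throughout.

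- Shown in the table: 1 − (1 − a)(1 − b)^(169/29)
- Under full collection: 1 − [(1 − a)(1 − b)]^(169/29)

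| a | b | Shown | Full collection |
|---|---|---|---|
| 5% | 1% | 10.4% | 30.1% |
| 10% | 1% | 15.1% | 49.0% |
| 20% | 2% | 28.9% | 75.8% |

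These gaps are upper-end illustrations, because the event rate probably falls once the acute infection has passed.

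**5. Grade 3–4 events**

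The protocol window is dosing to day 169. The SAP's windowed item covers days 30–169, so it leaves out the first 29 days. The unwindowed item could cover them, but does not say so.

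**The case against.** The strongest reply is that period 2 is a copying slip. Its own label contradicts it, the absence of any declared modification suggests that no change was intended, and the outputs carry their own limits. Much of this stands, and it rules out several stronger readings.

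- **That both the day-29 and the day-169 percentages are wrong.** The documents do not support this. Explicit windows bound the day-29 outputs. The day 1–169 percentages for serious events, grade 3–4 events, and events leading to hospitalisation or an emergency room visit rest on full collection.
- **That the secondary endpoint of serious events through day 29 is contaminated.** Its window is fixed in Protocol 4.2, SAP 1.2.4 and the SAP 5.8.1 item itself. None refers to period 2.
- **That the error carries into the treatment-emergent flag.** SAP 4.6.1 refers to the observation period without saying which, as the protocol does. The flag has to reach the end of follow-up in any case, because some event types are collected to day 169, and the full period is correctly defined for that.
- **That all grade 1–2 events stop at day 29.** Those that are serious, or lead to hospitalisation or an emergency room visit, are recorded to day 169.
- **That the SAP orders an any-grade table to day 169.** It does not do so in terms. Its only explicit all-event summary stops at day 29, and the items that name day 169 are event types collected that far. But the sentence on table divisions is unrestricted and the 5% and 10% lists have no window, so the text permits such outputs.

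On grade 3–4 events, the day-30 start mirrors the protocol's collection rule, and the unwindowed item could supply the protocol's summary. The protocol's window is still not stated anywhere in the SAP.

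**Conclusion.** Wrong as written, minor. The SAP's 29-day period contradicts the protocol and duplicates the full period. The practical risk is a programming error, mainly in items without their own window. Summaries programmed from their stated limits are correct.

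The unrestricted day 1–169 tables and the windowless frequency lists are a separate gap. An any-grade percentage to day 169 would omit other grade 1–2 events over 83% of the period. Collection is the same in every arm, so absolute percentages would mislead, but there is no differential bias between arms. How far they would mislead depends on event rates that the documents do not give.

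The protocol's grade 3–4 summary is not clearly carried over into the SAP. The primary efficacy analysis is not affected by any of this.

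**What to change.** In SAP 5.8.1:

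1. End the 29-day period at day 29, as in Protocol 11.4.5.1.
2. Restrict any-grade treatment-emergent tables, and the 5% and 10% lists, to days 1–29.
3. Limit day 1–169 tables to event types collected throughout: grade 3–4 events, serious events, deaths, and events leading to hospitalisation or an emergency room visit.
4. Report grade 3–4 treatment-emergent events for days 1–169, as the protocol specifies, and show days 30–169 as a split.

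The cost is SAP wording and table shells. Data collection and sample size do not change.

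### The SAP's primary safety analysis stops at SARS-CoV-2 vaccination, yet its day 1 to day 169 tables give percentages of all dosed patients with no censoring or time-at-risk rule

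*SAP*

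**What the plan says.** SAP 5.8.1 (Adverse Events) sets the rule: "For patients that are vaccinated for SARS-CoV-2, only the safety data before vaccination will be used in the primary safety analysis". The next sentence adds: "A secondary safety analysis will use all data collected". SAP 5.8 fixes the population: "The analysis of safety and tolerability will be performed in the SAF population". SAP 3.3 defines that set as everyone randomized and dosed, with no condition on vaccination or length of follow-up.

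The outputs in SAP 5.8.1 come in two lists. The first has dated items, among them "Treatment-emergent SAEs, up to day 169", "Treatment-emergent AEs (grade 3 or 4) from day 30 to day 169", and TEAEs that led to hospital or the emergency room, to day 169. The second asks for the number and percentage of patients with at least one SAE or AESI, and for "The number (n) and percentage (%) of patients with Grade 3 or Grade 4 treatment-emergent adverse events". The text after the lists says that in the adverse event tables "the observation period will be broken into two divisions: day 1 to day 29 and day 1 to day 169".

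The section's own period definition contains no cut: "The full observation period, i.e., from the time of the administration of the study drug to the last follow-up visit". Protocol 11.4.5.1 defines the full period in the same way and summarises grade 3 or 4 events through day 169, also uncut. Protocol 4.3 and SAP 1.2.4 list the proportion of patients with treatment-emergent SAEs through day 169 as an exploratory endpoint, again uncut. SAP 1.2.5 declares no modification from the protocol's statistical section.

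**The concern.** The numerator stops at vaccination and the denominator does not. Someone vaccinated before day 169 with no earlier event stays in the table as a patient without an event over 169 days, although the later part of that follow-up has been set aside. The resulting percentage is neither a day-169 proportion nor a pre-vaccination risk.

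Vaccination during follow-up is foreseeable. Protocol 8.10.1 discusses deferring it for at least 90 days after dosing, and Protocol 9.2.4.3 records SARS-CoV-2 vaccines as targeted concomitant medication. Protocol 3.2.1 extended follow-up to about 5 half-lives of about 30 days each so that safety could be assessed during elimination. For a patient vaccinated at 90 days, the primary safety data end at 90/30 = 3 half-lives. A reader of a primary table headed day 1 to day 169 would not know this.

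**Working it through.** The plan states no figure on this point, so there is none to reproduce. The check is a reading, one identity and an illustration.

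**1. Does a percentage to day 169 follow from the text?** The dated bullets do not themselves ask for n (%), and the n (%) bullets for SAEs, AESIs and grade 3 or 4 events carry no dates. The link is the later sentence that splits the tables into day 1-29 and day 1-169. It is an inference, but it is how the section would be programmed.

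**2. Is there a time-at-risk rule?** SAP 5.6 counts patients completing 29 and 169 days of follow-up but does not use those counts as a denominator. SAP 7.3 covers missing severity, causality and dates. Neither document mentions patient-time, censoring at vaccination or an at-risk denominator.

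**3. Direction.** In an arm of N patients in the safety set, let A be the number with a first event by day 169, and B the number of those whose first event is not after vaccination.

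- Uncut percentage = A/N; primary percentage = B/N.
- Gap = (A - B)/N, the share of patients whose first such event follows vaccination. It is never negative, and it is zero if there are no such patients.

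This applies to the SAE and AESI rows over day 1-169. Among AESIs it matters mainly for TEAEs leading to hospital or the emergency room, because the reaction categories end at day 4 or day 29.

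The day 30-169 grade 3 or 4 row is also cut, and a patient vaccinated before day 30 stays in its denominator with no usable time. That row also differs from the protocol's summary through day 169 because it starts at day 30. The gap formula therefore does not describe its distance from the protocol's figure.

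**4. Loss for one vaccinated patient.** SAP 7.4 sets study day = days since dosing + 1, so 90 days after dosing is day 91. Share of day 1-169 lost = (169 - 91)/169 = 78/169 = 46.2%.

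**5. Overall shortfall (illustration only).** Uptake u, a common vaccination day of 91 and the event pattern are all assumptions. For a rare event:

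- Constant rate: shortfall = u x 78/169.
- A share f of events by day 29, the rest uniform over the following 140 days: shortfall = (1 - f) x u x 78/140.

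| Uptake u | Constant rate | f = 0.5 | f = 0.8 |
|---|---|---|---|
| 20% | 9.2% | 5.6% | 2.2% |
| 40% | 18.5% | 11.1% | 4.5% |
| 60% | 27.7% | 16.7% | 6.7% |

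In patients: take an arm of 200 (SAP 2.1's planning figure, which presumes 1400 enrolled) and an assumed true day-169 proportion of 2%, that is 4 patients. At 40% uptake the primary table would show on average 4 x (1 - 0.185) = 3.3, 4 x (1 - 0.111) = 3.6, or 4 x (1 - 0.045) = 3.8.

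**The case against.** The strongest reply is that most of the remedy is already planned. The all-data analysis is announced in the sentence after the cut. Deaths, SAEs and every TEAE are listed, and SAP 5.3 summarises concomitant medications by arm. The cut also has a sensible purpose, since it keeps vaccine reactions apart from drug events. All of this stands, and it rules out the inference that late safety data are lost or hidden. It does not say what the primary day-169 percentage estimates.

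A second reply is that the tables are descriptive, and that crude percentages on the safety set also keep withdrawn patients in the denominator, so even the uncut figure is not a pure day-169 risk. That is true. But the cut adds a planned and foreseeable truncation to unplanned loss, under an unchanged label.

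A third is that the size is almost wholly assumed. That also stands. Uptake, timing and event rates are not in the documents, and enrolment closed at a number not given there. A reader might take the 22 days in Protocol 7.2.2 as a vaccination date and compute (169 - 23)/169 = 86% lost. That wording belongs to an exclusion for planned vaccination, and the same criterion cites deferral of at least 90 days, so 86% should not be read as an expected loss.

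Two further inferences are tempting. One is that the exploratory day-169 SAE endpoint will be taken from cut data. SAP 1.2.4 states that endpoint uncut, and SAP 5.8.1 does not say which analysis supplies it or which summaries make up the primary safety analysis. The other is that the comparison with placebo is biased. Patients and site staff are blinded, and nothing in the documents shows different uptake between arms.

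**Conclusion.** The point holds as a gap in definition and labelling that should be corrected. As written, the primary day 1-169 SAE and AESI percentages count vaccinated patients as event-free over time that the analysis discards, so they can only equal or understate the uncut percentages. The direction is certain given the reading in step 1. The only size that follows from the documents' day figures is the 46% of follow-up lost by a patient vaccinated at 90 days. The illustrated overall shortfalls, about 2% to 28% in relative terms, rest on the assumptions listed and are not bounds.

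The cut departs from the protocol's safety periods and summaries, and SAP 1.2.5 does not declare it. That is a minor point by itself, because Protocol 11 describes its statistical section as a summary on which the SAP is based.

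The consequence is limited. The only named day-169 safety endpoint is exploratory, and the secondary safety endpoints end at day 4 or day 29 and are little affected.

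**What to change.** Three edits to the SAP:

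1. In 5.8.1, state that the day-169 SAE proportion and every other percentage labelled to day 169 come from the all-data analysis already planned.
2. In 5.8.1, keep the pre-vaccination analysis and label it as such. Report its post-day-29 results as events per patient-time, or as a time-to-event estimate, censored at vaccination or last follow-up. Note that either approach assumes vaccination timing is unrelated to event risk.
3. Add time to vaccination by arm to 5.6, and declare the vaccination cut in 1.2.5.

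The cost is a few sentences and one line in the follow-up table. Vaccines are already recorded and both analyses are already planned, so no new data are needed. The downside is that the all-data day-169 tables will include vaccine reactions, which the retained pre-vaccination analysis continues to separate.
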